**Working Memory Task during fMRI:** Participants will complete a visual verbal **N-back Test** of working memory during the fMRI. This N-back task has three equivalent versions so that a different version will be administered on each study day. The specific version of the task will be counterbalanced across study days for each participant. These versions have been pilot tested with younger and older adults to ensure comparability of different versions and to ensure there is neither ceiling nor floor effects for performance for any age group.

*In this N-back task participants see a string of consonants (except L, W, and Y), presented in upper case letters, one every three seconds. Four conditions are presented: 0-back, 1-back, 2-back, and 3-back. The 0-back control condition had a minimal working memory load; participants are asked to decide if the current letter matches a single target letter that was specified before the epoch begins. In the 1-, 2-, and 3-back conditions, participants indicate whether the current letter on the screen matches a letter that is either 1, 2 or 3 back.*

*The 0-, 1-, 2-, and 3-back conditions are repeated three times in a counterbalanced order such that the same condition is not repeated two times in a row. In this block design task, participants respond to nine items in each block that takes 27 seconds. A rest break follows with a plus sign (+) fixation for 12*

seconds. The total time of the task is 8 minutes 12 seconds. Participants will practice the N-back task before drug dosing on each study day to ensure that they understood task instructions.

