**Analyses for fMRI Hypothesis Testing (H1b and H2b):** Preprocessing and analysis of the functional data will be performed with Brain Voyager QX software (Brain Innovation, Maastricht, The Netherlands). The volumes will be realigned to the first volume to minimize the effects of head movements. Further data preprocessing comprises spatial (6 mm full-width half-maximum isotropic Gaussian kernel) as well as

temporal (high pass filter: 2 cycles/run) smoothing to remove aliased signal correlated with background respiration and heart rate. Anatomical and functional images are co-registered and normalized to Talairach space. Statistical analysis will be performed by multiple linear regression of the signal time course at each voxel. The expected BOLD signal change for each different type will be modeled by a canonical hemodynamic response function. One mean image per individual for the task-based contrast of interest (e.g. 3-back > 0-back) will be created. These contrast images will then be used for second level multi-subject/between group analyses using the standard ANOVA procedures described above.

The critical significance level for the **fMRI** will be  $p_{corr} < 0.001$ . To begin with, **whole brain analyses** will be used *because our hypotheses are about changes in activation in the working memory network and restricting the analysis to a region of interest may miss important effects of the nAChR drugs on brain activation.*

**Additional Analysis:** We will examine the **correlation** between working memory performance and MFG activation by conducting a regression analysis based on the difference between the placebo and nAChR blockade or stimulation conditions. First, we will compute difference scores for the performance measures and the percent signal change for the MECA and NIC study days compared to the placebo day. The differences scores for activation will then be used as the dependent measures in the analyses, while the difference scores for performance measures will serve as independent variables.

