## **POTENTIAL RISKS**

**MECAMYLAMINE:** Mecamylamine is a centrally and peripherally active non-competitive antagonist of nicotine (and presumably acetylcholine) at C6 (ganglionic) type nicotinic receptors. Mecamylamine was in clinical use as an oral antihypertensive agent in the 1950's and is occasionally used today for autonomic disinhibition following such conditions as spinal cord injury. Peak cognitive and physiologic effects appear to occur by 2-3 hours and dissipate by 4-6 hours after oral administration. Mecamylamine (administered alone) can cause hypotension, changes in cardiac rate, decreased salivary secretions, decreased gastrointestinal tone and urinary hesitancy. Drs. [name], [name], [name], and [name] have used mecamylamine extensively in clinical studies in identical doses to those proposed here. We have occasionally observed prolonged (>6 hrs) asymptomatic orthostatic hypotension that they have treated conservatively by keeping the subject in bed and giving fluids. No sequelae have been observed and no other significant adverse events have occurred. There have been no clinically significant behavioral changes observed with this drug, and no long-lasting cognitive changes.

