**NICOTINE TRANSDERMAL PATCH:** At the nicotine dose proposed in this study, the major peripheral action of nicotine is facilitation of impulses through all autonomic ganglia, stimulation of the adrenal medulla and stimulation of sensory receptors including chemoreceptors in the carotid body. Ganglionic depression occurs at higher nicotine levels. In cardiovascular systems, mild increases in heart rate and blood pressure from sympathetic ganglion stimulation, catecholamine release from adrenal medulla, and aortic and carotid body chemoreceptor stimulation may occur. A mild parasympathetic response may be seen in the gastrointestinal tract and bladder (increased tone and motor activity), with increased secretion of exocrine glands. Nausea and vomiting can occur from peripheral (bowel activity and vagal efferent nerve stimulation) and central (medullary emetic chemoreceptor trigger zone stimulation) causes. Low dose stimulation of the CNS could in theory produce tremors and respiratory stimulation, although this is rarely seen except in patients with tremor disorders. Toxic nicotinic doses result in CNS depression. The most common adverse side effect of the nicotine transdermal patch is skin irritation and accounted for approximately 25 percent of adverse event reports regarding the nicotine transdermal patch to the FDA (Spyker et al. 1998). These effects consist of erythema, pruritus, edema, and rash. The PI and co-investigators have experience in administering transdermal nicotine for over ten years to non-smoking, healthy younger adults, healthy premenopausal women, and older patients with Mild Cognitive impairment. As the participants to be enrolled in this study will be selected for the absence of significant cardiovascular, cerebrovascular disease, or diabetes, we believe that the cardiovascular and cerebrovascular risk profile of transdermal nicotine in such participants is minimal.

**fMRI RISKS:** MRI has no known risks. Participants will be screened for metallic implants or any magnetic devices on or in their bodies prior to inclusion in the study. The MRI scanner produces a loud banging

noise and may be uncomfortable for some people who have claustrophobic-like reactions in confined spaces. Individuals will be allowed to terminate their participation should strong reactions occur. The long-term risks of functional MRI are unknown.

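### The 2-cycles/run high-pass filter cannot remove aliased cardiac and respiratory signal as the plan says, and no nuisance regressors are stated to take its place

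*Combined protocol and SAP*

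**What the plan says.** The paragraph on fMRI hypothesis testing (H1b and H2b), under Statistical Analysis, sets out the preprocessing. On motion: "The volumes will be realigned to the first volume to minimize the effects of head movements". It then lists spatial smoothing with a 6 mm kernel and a temporal high-pass filter of 2 cycles/run, described as "smoothing to remove aliased signal correlated with background respiration and heart rate". The purpose clause can be read as covering both smoothing steps. The first-level model follows: "Statistical analysis will be performed by multiple linear regression of the signal time course at each voxel", with a canonical haemodynamic response and one contrast image per person, for example 3-back > 0-back. The documents state no motion or physiological regressors, no censoring rule, no motion limit and no recording of pulse or breathing in the scanner. Vital signs are taken every 30 minutes but enter no imaging model.

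Under Methods and Procedures, the N-back task has 12 blocks (four conditions, three repeats each). On timing, "participants respond to nine items in each block that takes 27 seconds", each block is followed by 12 s of fixation, and "The total time of the task is 8 minutes 12 seconds".

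Under Potential Risks, mecamylamine "can cause hypotension, changes in cardiac rate", and with nicotine "mild increases in heart rate and blood pressure" may occur.

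**The concern.** A high-pass filter removes frequencies below its cut-off. Heartbeat and breathing are faster than a typical volume rate can follow, or close to its limit, so after sampling they can fold to almost any frequency up to the sampling limit. A filter that stops only the slowest drift therefore misses nearly all of them. Because the plan describes this signal as removed, it states no other step for it.

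This matters more than usual here because the challenge drugs act on the autonomic system and may alter heart rate. H1b and H2b concern drug effects on activation and how these differ between age groups. Noise left in the first-level contrasts carries into those tests, and its amount may not be the same on each drug day.

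**Working it through.** **Inputs from the documents.** Run length 8 min 12 s = 492 s. Filter 2 cycles/run. Blocks of 27 s plus 12 s fixation, 12 blocks, three per condition.

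**Assumptions.** The TR is not given; 1.5-3 s was tried. For the shares of rates below, heart rate 50-100 bpm and breathing 10-22/min. For the simulation, 55-90 bpm and 12-20/min, with the rate wandering by 3%.

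**1. Run length.** 12 × (27 + 12) = 468 s, which is 24 s short of the stated 492 s. Two extra 12 s fixations would explain the gap (an assumption). The cut-off hardly depends on this.

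**2. Cut-off.** 2/492 = 0.0041 Hz, a period of 492/2 = 246 s. With 468 s it is 2/468 = 0.0043 Hz.

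**3. Share of the usable band.** The band ends at 1/(2 × TR).

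| Assumed TR | Band limit (Hz) | Share below cut-off |
|---|---|---|
| 1.5 s | 0.333 | 1.2% |
| 2 s | 0.250 | 1.6% |
| 2.5 s | 0.200 | 2.0% |
| 3 s | 0.167 | 2.4% |

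**4. Where the signal lands.** A rate f aliases to |f − round(f × TR)/TR|. Over TR 1.5-3 s, only 0.9-2.3% of heart rates between 50 and 100 bpm alias below the cut-off. For breathing the share is 0% at TR 1.5-2.5 s and about 4% at 3 s.

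**5. Variance removed.** Aliased sinusoids (2,000 simulated runs per setting) were regressed on a constant, a linear trend and two sine/cosine pairs. The mean share removed was 1.8-3.6% of cardiac variance (median under 1%) and 0.01-4% of respiratory variance. Five such regressors take 5/(n − 1) of white noise, where n is the number of volumes: 1.5-3.1% over the same TRs. On cardiac signal, the filter does about what it would do to any noise.

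**6. Dependence on heart rate.** At an assumed TR of 2.5 s, 65, 70 and 75 bpm alias to 0.117, 0.033 and 0.050 Hz. All lie well above the cut-off. The 70 bpm value is close to the block cycle, 1/39 = 0.026 Hz. A modest change in heart rate can therefore move this noise nearer to or further from the task frequencies.

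**7. A higher cut-off is no remedy.** Each condition occurs three times per run, 3/492 = 0.0061 Hz, just above the present cut-off. A filter high enough to reach the physiological signal would remove task signal too.

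**8. Spatial smoothing.** A 6 mm kernel averages neighbouring voxels within a volume. It does not separate physiological from task fluctuations over time.

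**The case against.** The strongest reply is that the proven part is one wrong clause, and that rewording it changes no estimate or test. That is true of rewording alone. It is not true of adding a nuisance model that does the job the clause describes.

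Several further objections stand and limit the point.

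- **Bias.** A reader might infer that drug-related heart-rate change biases the drug-by-age contrast. The documents do not support this. The outcome is a within-run contrast with counterbalanced block order, and a heart-rate shift lasting the whole session is not locked to task load. A simulation of unfiltered aliased cardiac signal of unit amplitude (assumed TR 2 s, 3% wander) gave mean 3-back minus 0-back errors of −0.008, 0.001 and 0.000 at 60, 70 and 80 bpm. The spread varied with rate; the mean stayed near zero. Bias would need task-locked motion or physiology that differs by drug or age.
- **Drug effects.** A reader might infer that both drugs do change heart rate. The risk text says only that they can or may, and gives no size at the challenge doses.
- **Age.** No section says that motion or physiological noise differs between the age groups.
- **Motion.** A reader might infer that realignment is the only motion step. The document is an ethics-board form submitted with a full grant proposal, and its reference list includes a paper on motion correction in resting-state fMRI that the text does not cite. The fair statement is that no further step is stated here. Since the form calls itself the working protocol, it is reasonable to ask that the step be written into it.
- **Power.** The sample size section claims 90% power at a Type I error rate of 0.001 with 13 subjects for the age difference and 19 younger adults within group, against 48 per group planned. Taking 13 as per group (an assumption), the standard deviation could rise by √(48/13) = 1.9, or √(48/19) = 1.6, before the stated power was lost. The 0.40 standard deviation comes from pilot data, so it already contains whatever noise the pilot processing left.

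**Conclusion.** The filter does not do what the plan says. At 0.0041 Hz it removes drift and leaves nearly all aliased cardiac and respiratory signal at every TR tried (1.6-2.4% of the band covered at an assumed 2-3 s). That part rests on the plan's own run length and cut-off, plus an assumed TR that does not change the conclusion. The consequence that the documents support is extra noise in the first-level contrasts, in an amount that may vary by drug day. Its size cannot be computed, because there are no motion data and no heart-rate changes at the challenge doses. Systematic bias in H1b or H2b is a possibility that the documents neither describe nor allow to be sized. This is a worthwhile, low-cost improvement and not a threat to the trial.

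**What to change.** 1. Describe the high-pass filter as drift removal only, and leave its cut-off where it is.
2. Enter the six realignment parameters as nuisance regressors in every first-level model.
3. Add mean white-matter and CSF signals from the same images as physiological regressors, with a sensitivity analysis that leaves them out.
4. Tabulate motion by age group and drug day, so that any imbalance can be seen.

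No new data are needed. The cost is 6 + 2 = 8 degrees of freedom per run: 8/246 = 3.3% of volumes at TR 2 s (492/2 = 246) and 8/164 = 4.9% at 3 s (492/3 = 164). Some sensitivity is lost if motion is locked to the task blocks. This regressor set is one reasonable choice among several, and the documents hold no evidence of how well it would work here. Fixing it before the images are analysed also rules out choosing the noise model after seeing results.

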**Drug Challenge Procedures:** The three drug challenge days for each participant will be spread over no more than one month. No study day will follow a previous one by less than 48 hours. This time line has proven to be acceptable to participants for their time commitment to the study and does not negatively impact recruitment. The drug sequence will be determined by a random order procedure and will be balanced across the older and younger participant groups. Following an overnight fast, participants will report to the CRC at 0800 when the study will begin with baseline testing and evaluation. MECA or matching placebo will be administered at 0900. NIC or placebo patch will be administered at 1015 and removed immediately before scanning. fMRI scanning will begin at 1100. A double blind, double placebo system will be used. On the days that the MECA pill is active, the NIC patch is placebo and vice versa. Vital signs and pupil diameter will be recorded at 30 min intervals. Cognitive testing during functional neuroimaging will be conducted at 120 minutes after MECA dose and 45 minutes after NIC administration (1100). These times reflect previous data from our group ([name] et al. 2008, 2010; 2012; Carstens et al. 2011; [name] et al. 2009; 2012) on when CNS effects appear to be maximal following administration of nAChR agents. Participants will be transported by a nurse and the experimenter to the MRI suite for the fMRI session that will begin with the functional scans to maximize the drug dose timing. After scanning, participants will return to the CRC, complete mood assessment questionnaires (described below), and will receive lunch. Each participant will be followed until at least 1400, by which time the effects of the nAChR drugs will have dissipated. Participants will be checked for safety using a standard field sobriety test and if their vital signs are within normal limits, will be discharged.

**Figure 7.** Study Day Time Line

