### Statistical Analysis

**Analyses for Working Memory Performance Hypothesis Testing (H1a and H2a):** Comparisons of **MECA to placebo** will be conducted in support of **Hypothesis 1a**, while similar analyses comparing **NIC to placebo** will be used to test the hypotheses associated with **Hypothesis 2a**. The overall statistical model is:  $Y_{ijk} = \mu + s_{ik} + \pi_j + \tau_{t[i,j]} + \lambda_{d[i,j-1]} + x_k + \varepsilon_{ijk}$ , where  $Y_{ijk}$  is the value of the outcome of interest (**derived from the performance data described here and imaging data described below**) in subject k in sequence i at period j,  $\mu$  is the overall mean of the outcome of interest;  $s_{ik}$  is the effect of subject k in sequence i,  $i=1, 6$ ;  $\pi_j$  is the effect of period j,  $j=1, 3$ ;  $\tau_{t[i,j]}$  is the effect of treatment t,  $t=1, 2$  in period j of sequence i;  $\lambda_{d[i,j-1]}$  is the carryover effect of the treatment administered in period  $j_1$  of sequence i, where  $\lambda_{d[i,0]}=0$ ;  $x_k$  is the effect of baseline covariates for subject k; and  $\varepsilon_{ijk}$  is the random error (Jones and Kenward 2015). Because of the possibility of missing values in some of the measurements, we will employ a mixed effects model for these analyses, relying on the SAS proc mixed procedure for these analyses (Brown and Prescott, 2006).

**For this model, the effects of  $s_{ik}$  (subject) and  $\varepsilon_{ijk}$  (error) are considered random; all other effects are fixed.**

We will directly examine the effects of the drugs in older adults compared to younger adults. The mixed effects model will be adapted by the inclusion of additional variables to account for the effect of age group ( $g_{il}$  the effect of subject i in age group l; l=younger, older) and the treatment-by-age group interaction ( $g_{il} * \tau_{t[i,j]}$ ). The effect of interest in these analyses will be the interaction, which will test whether the effects of MECA or NIC differ with respect to the age of the subject. We predict there will be a significant interaction and will examine the age differences in response to the challenge drugs. For **performance analyses,  $p<0.05$**  will be used for statistical significance. We have used similar models in our prior work ([name] et al. 2012; [name] et al. 2009).

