For the correlational analyses, 48 subjects in each group will provide 90% power to detect a correlation of 0.46 as statistically significant and 80% power if the statistically significant correlation coefficient is 0.41.

**Risks/Benefits:** *Describe any potential or known risks. This includes physical, psychological, social, legal or other risks. Estimate the probability that given risk may occur, its severity and potential reversibility. If the study involves a placebo or washout period, the risks related to these must be addressed in both the protocol and consent. Describe the planned procedures for protecting against or minimizing potential risks and assess their likely effectiveness. Where appropriate, discuss plans for ensuring necessary medical or professional intervention in the event of adverse effects to the subjects. Discuss the potential benefits of the research to the subjects and others. Discuss why the risks to the subjects are reasonable in relation to the anticipated benefits to subjects and others. Discuss the importance of the knowledge gained or to be gained as a result of*

*the proposed research and why the risks are reasonable in relation to the knowledge that reasonably may result. If there are no benefits state so.*

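### The performance-activation regression on drug-minus-placebo differences states no period adjustment, so drift over the three study days in both measures could bias the correlation

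*Combined protocol and SAP*

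**What the plan says.** Under Statistical Analysis, the main mixed model has a term that "is the effect of period j" (three periods, fixed) and another that "is the carryover effect of the treatment administered in period" before. The section applies this model to outcomes from both the performance and the imaging data.

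The Additional Analysis paragraph that follows covers the link between performance and MFG activation. Its first step is to "compute difference scores for the performance measures and the percent signal change for the MECA and NIC study days compared to the placebo day". Activation differences are the dependent variable, and the "difference scores for performance measures will serve as independent variables". No period, sequence or carryover term is mentioned.

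On order, Drug Challenge Procedures says: "The drug sequence will be determined by a random order procedure and will be balanced across the older and younger participant groups". On size, Sample Size Calculations says that "48 subjects in each group will provide 90% power to detect a correlation of 0.46 as statistically significant". For a smaller correlation, 0.41, it claims 80%.

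**The concern.** Balanced order protects the mean drug effect, because day effects average out over sequences. It does not protect a covariance between two difference scores. With three days and six orders, the drug day lies one or two days before or after the placebo day, and the gap varies between participants. Any drift over days multiplies that gap and enters the performance difference and the activation difference of the same person. If both measures drift, the two differences share a component that is unrelated to the drug.

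Opposite drifts (accuracy up, activation down) push the correlation negative; drifts in the same direction push it positive. The analysis could therefore show a brain-behaviour link that does not exist, or hide one that does. The main model allows for period in both outcomes, so a regression run as literally written would be less protected than the analysis it supplements.

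**Working it through.** **Inputs from the documents.** 48 participants per age group; six sequences; SD 0.13 for accuracy and 0.40 for activation; within-person correlation 0.35; 3-back accuracy 0.75 (older) and 0.88 (younger).

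**Assumptions.** Eight participants per sequence; two-sided alpha 0.05 (none is stated for the correlation); correlation 0.35 for both measures; additive drift; normal errors. The SD of 0.40 is on the beta scale while the regression uses percent signal change, so only drift in SD units matters. No drift size is documented, so a range is shown.

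**1. The plan's power.** With Fisher's z, power = Φ(atanh(r)·√(n−3) − 1.96). At n = 48 this gives 91.6% for r = 0.46 and 83.2% for r = 0.41. The large-sample form Φ(r·√n − 1.96) gives 89.0% and 81.1%. The stated 90% and 80% are reproduced.

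**2. The shared gap.** Over the six orders, drug day minus placebo day is −2, −1, −1, +1, +1, +2. Its variance is v = (4+1+1+1+1+4)/6 = 2. If all learning falls between days 1 and 2, the steps are −1, −1, 0, 0, +1, +1 and v = 4/6 = 0.67.

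**3. Resulting correlation.** In SD units, the variance of a difference without drift is 2(1 − 0.35) = 1.3. Let d and a be the drift in accuracy and activation (SD per day, or SD for the single step), and ρ the true correlation of the differences. Then

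r = (1.3ρ + v·d·a) / √[(1.3 + v·d²)(1.3 + v·a²)].

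Example: 0.05 accuracy and −0.15 beta per day give d = 0.05/0.13 = 0.385 and a = −0.15/0.40 = −0.375. With ρ = 0, r = −0.288/√(1.596 × 1.581) = −0.18.

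**4. Type I error with ρ = 0** (simulation, one drug, one age group):

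| Assumed drift, accuracy / activation | Induced r | Raw differences | With period contrasts |
|---|---|---|---|
| None | 0 | 5% | 5% |
| One measure only, 0.5 SD/day | 0 | 5% | 5% |
| 0.1 SD/day in both | 0.015 | 5.1% | 5% |
| 0.2 SD/day in both | 0.06 | 6.7% | 5% |
| 0.03 / −0.09 per day (about 0.23 SD) | −0.07 | 8% | 5% |
| 0.05 / −0.15 per day (about 0.38 SD) | −0.18 | 24% | 5% |
| Day 1 to 2 only, 0.06 / −0.18 | −0.10 | 10% | 5% |
| Day 1 to 2 only, 0.10 / −0.30 | −0.23 | 36% | 5% |

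**5. Masking and lost power, true correlation −0.46.**
- Both measures drift upward: power on raw differences falls from 92% to 70% at 0.03/0.09 per day, and to 24% at 0.05/0.15 per day.
- Only accuracy drifts, 0.05 per day: |r| shrinks to 0.46·√(1.3/1.596) = 0.415. Power is about 85% raw and 91% adjusted.

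**6. Ceiling.** From 0.88, a gain of 0.05 per day reaches 0.98 on day 3, as does a single step of 0.10. With an SD of 0.13 on a proportion, unbounded additive drift of that size is not credible in younger adults. Older adults, at 0.75, would reach 0.85.

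**The case against.** The case on the other side is substantial.

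- **Size.** No document reports a practice or period effect for either measure. A reader might infer that ordinary practice by itself creates a false correlation. The documents do not support that: drift is needed in both measures, and small drift does little. In the 24% case, the assumed daily gain of 0.05 equals the whole mecamylamine effect that the plan assumes for younger adults (0.88 to 0.83).
- **Mitigation.** The task section provides practice before dosing on every study day, and three equivalent, pilot-tested versions counterbalanced over days. The activation measure is a task contrast such as 3-back against 0-back, so shifts common to both conditions cancel. These features should reduce drift. They do not show that it is absent: the stated purpose of the practice is understanding of the instructions, and equivalent versions do not remove general task learning.
- **Silence.** A reader might infer that the plan excludes period from this regression. It only fails to mention it. The Behavioral Measures section adds possible covariates to later analyses, so the Additional Analysis paragraph need not be a full covariate list.
- **Hypotheses.** A reader might infer that a negative artefact would count as support for the study hypotheses. Hypotheses 1a to 2b concern mean drug effects and age differences; none predicts a between-person correlation. The tests of those hypotheses through the main model keep their period term.

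These points limit the size and reach of the problem. They do not answer the algebra: balanced order leaves the covariance unprotected, and the text as written gives the analyst no instruction to adjust.

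**Conclusion.** The point holds in conditional form. The additional regression states no period adjustment, and if accuracy and MFG activation both drift over days, its correlation is biased, in a direction set by the signs of the drifts. Type I error is about 5% to 8% for linear drift up to roughly 0.2 SD per day in both measures. It is about 24% to 36% for large drift, which is implausible in younger adults because of ceiling. With drift in one measure only, there is no false correlation, but some power is lost.

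The mechanism is certain. Its size is entirely assumed, and rests on equal sequence sizes, additive drift and the plan's SDs and correlation. This is a supporting analysis, and the main-model tests of the hypotheses are unaffected. The change is worth making because it costs so little.

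**What to change.** In the Additional Analysis regression, for each drug, add two covariates per participant: the period-2 indicator of the drug day minus that of the placebo day, and the same for period 3. Alternatively, residualise both difference scores on these same two contrasts in the same participants, and test with matching degrees of freedom (48 − 4 = 44 instead of 46). Residuals from the main mixed model should not be used as an equivalent: that model also removes treatment and carryover, shrinks the subject effects and uses all three days. The plan should also say whether carryover enters this regression, since it too is in the main model and unmentioned here.

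The cost is a sentence or two in the plan and 2 degrees of freedom. Simulated power without drift goes from about 92% to 91% at r = 0.46, and from about 84% to 82% or 83% at r = 0.41. The stated 90% and 80% still hold with 48 per group.
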